6.8 CONCOMITANT THERAPY

Any medication or vaccine (including over-the-counter or prescription medicines, vitamins and/or herbal supplements, or other specific categories of interest) or procedures that the participant is receiving at the time of enrollment or receives during the study must be recorded along with:

- Reason for use
- Dates of administration, including start and end dates
- Dosage information, including dose and frequency

The Medical Monitor should be contacted if there are any questions regarding concomitant or prior therapy.

Prohibited medications

The following concomitant treatments are not permitted during the Screening Period and throughout the study unless otherwise specified:

- Intranasal corticosteroids within 5 half-lives or at least 30 days, whichever is longer, before Visit 1, during the Screening Period, and up to Week 52 (however, INCS can be used for other coexisting diseases [eg, allergic rhinitis] after Week 24, as needed, to keep more participants for the assessment of exploratory endpoints with 52-week treatment)

- Any systemic immunosuppressive treatment, including but not limited to methotrexate, cyclosporine, mycophenolate, tacrolimus, gold, penicillamine, sulfasalazine, hydroxychloroquine, azathioprine, and cyclophosphamide, within 4 weeks before Visit 1 or 5 half-lives, whichever is longer, during the Screening Period, and up to Week 52
- Anti-IgE therapy (omalizumab) within 4 months before Visit 1, during the Screening Period, and up to Week 52 and other biologics for immuno-inflammatory conditions within 4 weeks before Visit 1 or 5 half-lives, whichever is longer, and up to Week 52
- Allergen immunotherapy during the Screening Period and up to Week 52 (except if initiated more than 3 months prior to Visit 1 and dose stable for 1 month prior to Visit 1)
- Long-term courses (>2 weeks) of SCS are prohibited from Visit 1 onward
- Short-term courses (≤ 2 weeks) of SCS are prohibited only during the Screening Period, and they are allowed as rescue medication after Visit 2
- Live, attenuated vaccines within 4 weeks before Visit 1, during the Screening Period, and up to Week 52 (Appendix 8 [[Section 10.8](#)])
- Systemic antibiotic for >2 weeks during the study
- Use of intranasal decongestants, except for preparation of nasal endoscopy (NE)

Participants who receive any of the prohibited treatments or undergo surgery during the Screening Period will not start the intervention period. They may, however, be rescreened following the procedures described in the SoA ([Section 1.3](#)).

Participants who use INCS between Visit 2 and Week 24 for whatever reason will discontinue the IMP administration.

Permitted concomitant medication

The following treatments are allowed throughout the study unless otherwise specified:

- Intranasal corticosteroids to treat other coexisting diseases (such as allergic rhinitis) are allowed after Week 24 as needed.
- Nasal normal saline.
- Single topical decongestant administration such as oxymetazoline hydrochloride (to reduce swelling and widen the path for the endoscope) and topical anesthetics such as lidocaine are allowed before endoscopy.
- Short-acting $\beta 2$ -adrenergic receptor agonists, long-acting $\beta 2$ -adrenergic receptor agonists, and long-acting muscarinic acetylcholine receptor antagonists.
- Methylxanthines (eg, theophylline, aminophyllines).
- Inhaled corticosteroids.
- Systemic antihistamines.

- Leukotriene antagonists/modifiers are permitted during the study, only for participants who were on a continuous treatment for ≥ 30 days before Visit 1.
- Allergen immunotherapy in place for ≥ 3 months before Visit 1 is permitted.
- Paracetamol/Acetaminophen, at doses of ≤ 2 g/day, is permitted for use any time during the study.

Other concomitant medication may be considered on a case-by-case basis by the Investigator in consultation with the Medical Monitor if required.

Rescue medication including antibiotics, short courses of SCS for treatment of CRSwNP as described in [Section 6.8.1](#), or short courses of SCS to treat other serious coexisting diseases (such as asthma exacerbation) or for AEs is allowed.

6.8.1 Rescue medicine and procedures

During the study intervention period, based on clinical evaluation, in case of worsening of signs and/or symptoms requiring medical intervention, the following rescue medications/procedures may be employed as per Investigator's judgment:

1. Systemic (eg, oral) corticosteroids up to 2 weeks
2. Antibiotics for the treatment of acute sinusitis less than 2 weeks after Visit 2
3. Sinonasal surgery

Participants receiving rescue treatment other than surgery during the study should continue on IMP unless the Investigator decides to withdraw the study intervention. Before starting treatment with SCS, participants should come to the study site for the clinical assessments including endoscopy.

For participants who undergo or plan to have surgery for NP, the Investigator may decide to continue IMP up to the time of surgery or EOT, whichever date comes first. At the time of surgery, participants will be permanently discontinued from study intervention and assessed as soon as possible using the procedures normally planned for the EOT/EOS Visit as described in the SoA ([Section 1.3](#)).

If the surgery is to be performed during the intervention period, an AE or SAE page will be completed. If surgery is scheduled after the planned EOS, the EOT/EOS Visit will not be delayed. The surgery will be followed up by the Investigator or the participant's physician with general medical practice.

In any case, participants who prematurely discontinue the treatment will be encouraged to return to the study site for the efficacy and safety assessments planned at the EOT/EOS Visit (refer to SoA [[Section 1.3](#)]).

The date and time of rescue medication administration as well as the name and dosage regimen of the rescue medication must be recorded. For participants who undergo sinonasal surgery for NP, the reason (worsening signs and/or symptoms during the study), the expected and real surgery

dates, and the type and outcome of surgery will be recorded. For participants who plan to have sinonasal surgery for NP, the reason (worsening signs and/or symptoms during the study), the expected and real surgery dates, and the type of surgery will also be recorded in the e-CRF.

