7.1.1 Permanent discontinuation

In rare instances, it may be necessary for a participant to permanently discontinue study intervention. If study intervention is permanently discontinued, the participant will remain in the study to be evaluated for the assessments planned for the EOT/EOS Visit, with the exception of the CT scan. See the SoA ([Section 1.3](#)) for data to be collected at the time of discontinuation of study intervention and follow-up and for any further evaluations that need to be completed.

Participants must be withdrawn from the study (ie, from any further IMP or study procedure) for the following reasons:

- At their own request or at the request of their LAR (an individual or judicial or other body authorized under applicable law to consent on behalf of a prospective participant to the participant's participation in the procedures involved in the research)
- If, in the Investigator's opinion, continuation in the study would be detrimental to the participant's well-being
- In case of surgery for NP
- At the specific request of the Sponsor
- In the event of a critical protocol deviation, at the request of the Investigator or the Sponsor
- In the event of an anaphylactic systemic allergic reaction that is related to IMP and that requires treatment
- In the event that the participant is diagnosed with a malignancy during the study, excluding carcinoma in situ of the cervix or squamous or basal cell
- Pregnancy
- Any opportunistic infection, such as TB or other infections whose nature or course may suggest an immunocompromised status (refer to Appendix 9 [[Section 10.9](#)])
- Met liver chemistry stopping criteria ([Section 7.1.2](#))

Handling of participants after permanent intervention discontinuation

Participants will be followed up according to the study procedures specified in this protocol up to the scheduled date of study completion or up to recovery or stabilization of any AE to be followed up as specified in this protocol, whichever comes last.

If possible, and after the permanent discontinuation of intervention, the participants will be assessed as soon as possible using the procedures normally planned for the EOT/EOS Visit (refer to SoA [[Section 1.3](#)]).

All cases of permanent intervention discontinuation must be recorded by the Investigator on the appropriate pages of the e-CRF when considered as confirmed.

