#### **4.4.1.2 Main analytical approach**

##### Handling of missing data

Each of the 3 key secondary efficacy endpoints will be analyzed using the PP population and a hybrid method of worst observation carried forward (WOCF) and multiple imputation. For participants taking rescue medications or who undergo surgery, their data after the medication usage or surgery will be set to missing, and the worst postbaseline value on or before the time of the medication usage or surgery will be used to impute the missing Week 24 value. Participants who discontinue the treatment prematurely are encouraged to follow the planned clinical visits, and in those participants who did not take rescue medications or undergo surgery, all data collected after treatment discontinuation will be used in the analysis. For these participants, missing data may still happen despite all efforts to collect the data after treatment discontinuation. For participants who discontinue due to lack of efficacy, all data collected after discontinuation will be used in the analysis, and a WOCF approach will be used to impute the missing Week 24 value if needed. For participants who discontinue not due to lack of efficacy, a multiple imputation approach assuming missing at random will be used to impute the missing Week 24 value, and this multiple imputation will use all participants, excluding participants who have taken rescue medications or undergone surgery on or before Week 24 and excluding participants who discontinue due to lack of efficacy on or before Week 24. All of the imputed complete data will be analyzed by descriptive statistics with the 95% CI. The summarized mean changes obtained from each imputed dataset will be combined using Rubin's rule for a single estimate.

The following steps will be used to create the primary imputed datasets:

- Impute any missing baseline values with the mean baseline value of all participants with non-missing baseline data.
- For participants who are rescued (undergo surgery for NP or receive SCS for any reason) or discontinue treatment early due to lack of efficacy:
  - Set all data on or after earliest date of rescue or treatment discontinuation to missing.
  - Replace all missing values with the worst observation prior to the missing data through Week 24, including baseline values.
- For participants who are not rescued, discontinue treatment for reasons other than lack of efficacy, or complete the study:

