### **4.5.2.3 Same as primary and secondary endpoints**

Primary and secondary endpoints up to Week 24 will be summarized each visit. These endpoints after Week 24 up to Week 52 will be summarized each visit by dose regimen group and overall. Imputation will not be used.

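### An endoscopy is required before corticosteroid rescue but not secured before sinonasal surgery, and the unimputed by-visit summaries do not remove post-operative scores

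*Protocol*

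**What the plan says.** For SCS rescue, Protocol 6.8.1 is explicit: "Before starting treatment with SCS, participants should come to the study site for the clinical assessments including endoscopy". For surgery, the same section says that "the Investigator may decide to continue IMP up to the time of surgery or EOT, whichever date comes first", and then: "At the time of surgery, participants will be permanently discontinued from study intervention and assessed as soon as possible". The procedures are those of the EOT/EOS visit. Protocol 7.1.1 also places this assessment after treatment has stopped: "If possible, and after the permanent discontinuation of intervention, the participants will be assessed as soon as possible". The same section lists "In case of surgery for NP" among the reasons for withdrawal from further drug and further study procedures, and exempts participants who stop treatment from the CT scan.

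The analysis rules for surgery are:

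- **Primary endpoint (Protocol 9.3.2, SAP 4.3.2):** operated participants are nonresponders at time points after surgery.
- **Key secondary endpoints, narrative (Protocol 9.3.3, SAP Table 3 and 4.4.1.2):** "their data after the medication usage or surgery will be set to missing", and the worst value up to and including the time of surgery replaces Week 24. Protocol 9.3.3 and Table 3 fall back on baseline only if no postbaseline value exists.
- **Key secondary endpoints, programming steps (SAP 4.4.1.2):** values dated on the day of rescue or of treatment stop, whichever is earlier, are deleted along with all later ones. The worst remaining value is carried forward, with baseline among the candidates.
- **By-visit summaries (SAP 4.5.2.3):** "Imputation will not be used". Nothing is said about values obtained after surgery.

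**The concern.** Surgery removes the polyps that the NPS counts, so an endoscopy before the operation and one after it measure different things. If study drug runs up to the operation and the EOT/EOS visit follows discontinuation, nothing ensures that the deterioration leading to surgery is scored.

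Two things follow. First, the worst-value rule can only use scores that exist, so the imputed value may be milder than the participant's state at surgery. Second, a post-operative score that falls inside a visit window can enter the unimputed tables as an observed improvement. The study has one arm and compares its point estimates with EFC14280, so no concurrent control would offset either effect.

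**Working it through.** **The plan's own figure.** Inputs from Protocol 9.1: true responder rate 62.0%, target an observed rate of at least 50%, n = 20, 20% drop-out. The exact binomial P(X ≥ 10 | n = 20, p = 0.62) is 0.9077, in line with the stated 90%. Drop-out: 20/(1 − 0.20) = 25. Both figures reproduce.

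**Primary endpoint.** A participant operated on before Week 24 is a nonresponder whether the EOT/EOS endoscopy comes before or after surgery. The shift from its timing is 0 points, and the sample size does not change.

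**Age of the last score.** Postbaseline endoscopy is at Visits 4 to 9, on Days 29, 57, 113, 169, 281 and 364. Ignoring visit windows, the longest gaps are:

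- before Week 24: 113 − 57 = 56 and 169 − 113 = 56 days (8 weeks);
- Weeks 24 to 40: 281 − 169 = 112 days (16 weeks);
- Weeks 40 to 52: 364 − 281 = 83 days.

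**Effect on mean NPS change at Week 24.** Let d be the points by which the unrecorded NPS exceeds the value carried forward, k the number operated on, and n the number analysed. The mean looks too favourable by k·d/n. For k = 1:

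| d (assumed) | n = 20 | n = 25 |
|---|---|---|
| 1 | 0.05 | 0.04 |
| 2 | 0.10 | 0.08 |
| 3 | 0.15 | 0.12 |

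Two such participants double these values. With baseline among the candidates, as in the SAP steps, d counts only points above baseline and above every earlier score. With a baseline of at least 5 out of 8, d is at most 8 − 5 = 3. That floor applies to the Visit 1 central and Visit 2 local readings. The analysis baseline is the Visit 2 central reading, which could be lower.

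**Why the wording of the rule matters.** Assume baseline 6, every postbaseline score 4, and 7 just before surgery.

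- Postbaseline values only: 4 is carried forward, change −2, so d = 7 − 4 = 3; 3/25 = 0.12 (3/20 = 0.15).
- Baseline included: 6 is carried forward, change 0, so d = 7 − 6 = 1; 1/25 = 0.04 (1/20 = 0.05).

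The same participant differs by 2/25 = 0.08 (2/20 = 0.10) between the two wordings.

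**Would a pre-operative visit be used as the SAP stands?** Not always. The narrative keeps a value from the day of surgery; the steps delete it. For a rescued participant the steps also cut at treatment stop if that is earlier, so a visit between the last dose and the operation would be lost too.

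**By-visit summaries.** The endoscopy column of SAP Table 10 assigns Days 141 to 224 to Week 24. A post-operative endoscopy on Day 155 is therefore a Week 24 value. Assume NPS falls from 6 to 0 at surgery and n = 25:

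- against an NPS that would have stayed at 6: −6/25 = −0.24 in the mean change;
- against leaving the value out, with the others' mean change at −2 (assumed): (−6 − (−2))/25 = −0.16;
- in the responder rate, only if the nonresponder rule were not applied: 1/25 = 4.0 points (1/20 = 5.0 points).

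**The case against.** The strongest reply is that every formal endpoint analysis already handles surgery. Operated participants are nonresponders in the primary analysis and at Week 52, and post-surgery values are discarded in the continuous analyses. Discarding them is the stated strategy for this event. The rule carries forward the worst value, not the last, and the SAP steps include baseline, so an operated participant is credited with no improvement at Week 24 under those steps. All of this stands, and it is why the effect is small.

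A reader might go further and infer that the protocol requires the assessment to follow the operation, that the pre-surgery state is never measured, and that surgery then counts as improvement. The documents do not support this. The wording does not say on which side of the operation the visit falls, and study drug may be stopped earlier. An unscheduled evaluation visit is available, although it is optional and names no endoscopy. Scheduled endoscopies that precede surgery also record earlier states. What can be said is that a pre-operative score is not secured.

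On the by-visit responder tables, the nonresponder rule is worded by time point, and SAP Table 3 treats it as a composite strategy needing no further imputation. It may therefore carry over to SAP 4.5.2.3 despite the ban on imputation, but that section does not say so. For the continuous by-visit summaries no rule removes a post-operative value.

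**Conclusion.** The point holds as a limited gap in measurement and reporting. Surgery lacks the endoscopy step that SCS rescue has, so the worst-value rule may work from a score up to 8 weeks old before Week 24, or up to 16 weeks old between Weeks 24 and 40. The primary result and the sample size do not move. Mean NPS change could look better by about 0.04 to 0.15 per operated participant, assuming 1 to 3 unrecorded points beyond all earlier values and 20 to 25 analysed. The postbaseline-only wording could make this larger.

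The separate gap in SAP 4.5.2.3 is real for the continuous summaries and unresolved for the responder tables. The documents do not give an expected number of operations, so all sizes are per participant. The post-operative score of 0 is an illustration.

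**What to change.** 1. **Protocol 6.8.1 and the Schedule of Activities:** state that for planned NP surgery the EOT/EOS efficacy assessments (endoscopy with central reading, VAS, diary check) are done before the operation where feasible, and record their timing relative to surgery. This is the same visit placed earlier, and expected and actual surgery dates are already collected. An urgent operation may leave no time for it. The decision to operate is not affected.
2. **SAP 4.4.1.2:** align the programming steps with the narrative and Table 3, so that a pre-operative value is kept for the worst-value rule even if taken on the day of surgery or on or after the day study drug stops. State in one place whether baseline is a candidate for the worst value. Without this change, item 1 may add nothing to the analysis.
3. **SAP 4.5.2.3:** remove post-surgery values from the continuous by-visit summaries and show how many were removed. Keep operated participants as nonresponders in the by-visit responder tables. Excluding them would hide treatment failures: with one of 25 operated on and 62% response among the other 24, the rate is 0.62 × 24/25 = 59.5% if that participant counts as a nonresponder, but 62% if excluded.
4. **Protocol 6.8.1 and 7.1.1:** reconcile the two sections. One calls for EOT/EOS procedures at surgery; the other lists surgery as a reason to end all further study procedures and omits the CT scan after discontinuation.

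The cost is a short protocol clarification and a few SAP sentences.

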7 DISCONTINUATION OF STUDY INTERVENTION AND PARTICIPANT DISCONTINUATION/WITHDRAWAL

7.1 DISCONTINUATION OF STUDY INTERVENTION

The IMP should be continued whenever possible. In case the IMP is stopped, it should be determined whether the stop can be made temporarily; permanent IMP discontinuation should be a last resort. Any IMP discontinuation should be fully documented in the e-CRF. In any case, the participant should remain in the study as long as possible.

7.1.1 Permanent discontinuation

In rare instances, it may be necessary for a participant to permanently discontinue study intervention. If study intervention is permanently discontinued, the participant will remain in the study to be evaluated for the assessments planned for the EOT/EOS Visit, with the exception of the CT scan. See the SoA ([Section 1.3](#)) for data to be collected at the time of discontinuation of study intervention and follow-up and for any further evaluations that need to be completed.

Participants must be withdrawn from the study (ie, from any further IMP or study procedure) for the following reasons:

- At their own request or at the request of their LAR (an individual or judicial or other body authorized under applicable law to consent on behalf of a prospective participant to the participant's participation in the procedures involved in the research)
- If, in the Investigator's opinion, continuation in the study would be detrimental to the participant's well-being
- In case of surgery for NP
- At the specific request of the Sponsor
- In the event of a critical protocol deviation, at the request of the Investigator or the Sponsor
- In the event of an anaphylactic systemic allergic reaction that is related to IMP and that requires treatment
- In the event that the participant is diagnosed with a malignancy during the study, excluding carcinoma in situ of the cervix or squamous or basal cell
- Pregnancy
- Any opportunistic infection, such as TB or other infections whose nature or course may suggest an immunocompromised status (refer to Appendix 9 [[Section 10.9](#)])
- Met liver chemistry stopping criteria ([Section 7.1.2](#))

Handling of participants after permanent intervention discontinuation

Participants will be followed up according to the study procedures specified in this protocol up to the scheduled date of study completion or up to recovery or stabilization of any AE to be followed up as specified in this protocol, whichever comes last.

If possible, and after the permanent discontinuation of intervention, the participants will be assessed as soon as possible using the procedures normally planned for the EOT/EOS Visit (refer to SoA [[Section 1.3](#)]).

All cases of permanent intervention discontinuation must be recorded by the Investigator on the appropriate pages of the e-CRF when considered as confirmed.

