- a Past medical history, including allergic comorbidities (asthma, aspirin sensitivity, allergic rhinitis, etc.). Surgeries for NP, including number, type and dates of sinonasal surgeries, and polypectomies, in the past will be recorded. Systemic corticosteroid use (number of courses, doses, route of administration, and duration) in the past 2 years before V1 and/or contraindication/intolerance to SCS, as well as long-term antibiotics use (>2 weeks) in the previous year, will be entered in the e-CRF. NERD will be assessed through a specific questionnaire (Appendix 11 [Section 10.11]).
- b Call IVRS/IWRS to register visit and obtain next IMP kit numbers assignment or report potential definitive IMP stop.
- c Investigational medicinal product will be administered q2w (after Week 24, some participants can be administered q4w). Between visits, at site or home administration is allowed after the second dose. Investigational medicinal product will be administered after the completion of all scheduled clinical assessments at the visit or at home. The planned last dose is at Week 48 or 50. For participants who have stable disease at Week 24, the dosing interval can be changed from q2w to q4w at the discretion of the Investigator; the reason for the change in dosing regimen should be recorded in the e-CRF. Other participants will receive the q2w regimen until Week 50. Stable disease is defined as NPS improvement from baseline to both Weeks 16 and 24 of ≥ 2 points.
- d Nasal endoscopy: endoscopy (including use of decongestants before the procedure) will be performed after all other efficacy assessments have been completed for each visit. Standard video sequences will be downloaded by the Investigator to the central reader's secured internet site. For eligibility, central reading of V1 will be used. At V2, the Investigator will review the V1 results from the central reader to confirm entry criteria and reconfirm eligibility based on a review of the inclusion/exclusion criteria and the V2 endoscopy local reading. To confirm eligibility at V2, only the V1 central reading will be made available to the site. In addition, at V2, the Investigator will perform the NE to confirm eligibility score and enter the result in the e-CRF. Thus, the participant will be considered eligible based on a V1 central reading followed by a V2 local reading NPS score of 5 or more and at least 2 on each side.
- e Computerized tomography scan to be done during the Screening Period.

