8.1.3 Computerized tomography scan: Lund Mackay score

The LMK system is based on localization with points given for degree of opacification: 0 = normal, 1 = partial opacification, 2 = total opacification. These points are then applied to the maxillary, anterior ethmoid, posterior ethmoid, sphenoid, and frontal sinus on each side. The osteomeatal complex (OC) is graded as 0 = not occluded or 2 = occluded. Adding the scores of these 6 parameters will derive a maximum score of 12 per side (left and right). The total score of the 2 sides will be used for analysis. This scoring system has been validated in several studies (8, 9, 10).

For participants in whom the OC is missing (because of a previous surgery), the reader should consider the location of the previous OC and provide a score (as if the OC were there).

Computerized tomography scan should be performed anytime during the Screening Period before the first administration of IMP and at Visits 7 and 9 (Weeks 24 and 52). Whenever possible, a cone beam CT scan should be utilized.

Details for CT will be available in a separate operational manual provided to the sites.

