9.3.3 Key secondary efficacy endpoints

- Change from baseline to Week 24 in bilateral NPS
- Change from baseline to Week 24 in NC symptom severity score using the CRSwNP nasal symptom diary (refer to [Section 8.1.2](#) for the details of NC symptom severity score assessment)
- Change from baseline to Week 24 in opacification of sinuses assessed by CT scan using the LMK score (refer to [Section 8.1.3](#) for the details of LMK score)

Handling of missing data

Each of the 3 key secondary efficacy endpoints will be analyzed using a hybrid method of worst-observation carried forward (WOCF) and multiple imputation. For participants taking selected prohibited medications and/or rescue medications or who undergo surgery (details of selection will be specified in the SAP, refer to [Section 6.8.1](#)), their data after the medication usage or surgery will be set to missing, and the worst postbaseline value on or before the time of the medication usage or surgery will be used to impute the missing Week 24 value (for participants whose postbaseline values are all missing, the baseline will be used to impute). Participants who discontinue the treatment prematurely are encouraged to follow the planned clinical visits, and in those participants who did not take the selected prohibited medications and/or rescue medications or undergo surgery, all data collected after treatment discontinuation will be used in the analysis. For these participants, missing data may still happen despite all efforts to collect the data after treatment discontinuation. For participants who discontinue due to lack of efficacy, all data collected after discontinuation will be used in the analysis, and a WOCF approach will be used to impute the missing Week 24 value if needed. For participants who discontinue not due to lack of efficacy, a multiple imputation approach assuming missing at random will be used to impute the missing Week 24 value, and this multiple imputation will use all participants, excluding participants who have taken the selected prohibited medications and/or rescue medications or undergone surgery on or before Week 24 and excluding participants who discontinue due to lack of efficacy on or before Week 24. All of the imputed complete data will be analyzed by descriptive statistics with the 95% CI. The summarized mean changes obtained from each imputed dataset will be combined using Rubin's rule for a single estimate.

Other secondary efficacy endpoints

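### Protocol 7.1.1 gives conflicting CT rules for participants who permanently stop study drug, and the wide Week 24 CT window in SAP Table 10 lets an early-stop scan stand as the Week 24 LMK score

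*Protocol*

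**What the plan says.** Protocol 7.1.1 contains three instructions for a participant who permanently stops study drug.

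- The opening paragraph keeps the participant in the study to be "evaluated for the assessments planned for the EOT/EOS Visit, with the exception of the CT scan".
- The part on handling after discontinuation says: "Participants will be followed up according to the study procedures specified in this protocol up to the scheduled date of study completion". It makes no exception for the CT.
- The same part adds that, if possible, "the participants will be assessed as soon as possible using the procedures normally planned for the EOT/EOS Visit". Again there is no exception.

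Protocol 6.8.1 gives the third instruction to participants who have surgery for nasal polyps: they are to be "assessed as soon as possible using the procedures normally planned for the EOT/EOS Visit as described in the SoA". The SoA marks a CT at Visit 9, which is the EOT/EOS Visit, and Protocol 8.1.3 schedules scans at screening, Visit 7 (Week 24) and Visit 9 (Week 52). The only SoA footnote on the CT reads "Computerized tomography scan to be done during the Screening Period" and says nothing about discontinuers.

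On the analysis side, Protocol 9.3.3 makes the change in LMK to Week 24 a key secondary endpoint. For participants who stop treatment without rescue or surgery, "all data collected after treatment discontinuation will be used in the analysis"; SAP Table 3 labels this a treatment policy strategy. SAP Table 10 gives the Week 24 CT a target day of 169 and a window from after the first dose to day 265. SAP 5.4.5 takes the measurement closest to the target day when there are several, and treats the visit as missing when there is none.

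**The concern.** A site can follow one sentence of 7.1.1 and depart from another. For LMK the choice carries through to the analysis, because no CT is scheduled between screening and Week 24 and the Week 24 window opens straight after the first dose. If a participant stops early and has no Visit 7 scan, a scan taken at the stop, even after a few weeks of treatment, is analysed as Week 24. If the site applies the CT exception, there is no scan and the value is imputed. Two sites could handle the same kind of participant differently in a study of about 25 people, and neither result is the score at Week 24 that a treatment policy strategy calls for.

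**Working it through.** **The plan's own figure.** The sample-size statement uses a 62.0% responder rate, 20 evaluable participants and a criterion of at least 50%. The exact binomial probability P(X ≥ 10) with n = 20 and p = 0.62 is 0.9077, which agrees with the stated 90%. Inflation for drop-out gives 20 / (1 - 0.20) = 25. All that is needed from this is the planned number of drop-outs: 25 - 20 = 5.

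**What each sentence leads to.** This is for a non-rescued participant who stops before Week 24 for a reason other than lack of efficacy. The rules in SAP 5.4.5 are taken to apply to the CT column of Table 10, although the lead sentence there names only VAS, vital signs and laboratory data.

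| Sentence followed | Scans available | Week 24 LMK in the analysis |
|---|---|---|
| CT excepted, no Visit 7 scan | Screening only | Missing, multiply imputed |
| EOT/EOS procedures in full, no Visit 7 scan | Screening and early scan | Early scan, because it lies in the window up to day 265 |
| Follow-up continues, Visit 7 scan done | Scan near day 169, with or without an early scan | Visit 7 scan, being closest to target |

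**Who is affected.**

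- Surgery or other rescue: SAP 4.4.1.2 sets later data to missing and carries the worst observation forward. The site's choice of sentence makes no difference.
- Stopped for lack of efficacy: the SAP 4.4.1.2 prose uses data collected after the stop, but its imputation steps set them to missing and carry the worst value forward. This group is unclear.
- Stopped because of INCS use before Week 24: excluded from the PP population, which is the main LMK analysis set.
- Visit 7 scan done: not affected, by the closest-to-target rule.

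That leaves non-rescued PP participants who stop before Week 24, mainly for reasons other than lack of efficacy, and who have no Visit 7 scan.

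**Size.** The documents give no LMK effect or SD, so these are assumptions: mean change C = -5 in the other participants, change E = -1 to -4 at the early scan, SD 4. Let k be the number affected out of 25.

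- Early scan used: mean = [(25 - k)C + kE] / 25.
- No scan: the imputation has only baseline LMK to draw on, so with similar baselines the expected mean is about C.
- Shift between the two = k(E - C) / 25, where E - C runs from 1 to 4.
- SE = 4 / √25 = 0.8.

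| k | Shift in mean LMK change (points) | Shift / SE |
|---|---|---|
| 1 | 0.04 to 0.16 | 0.05 to 0.2 |
| 2 | 0.08 to 0.32 | 0.1 to 0.4 |
| 5 (all planned drop-outs) | 0.2 to 0.8 | 0.25 to 1.0 |

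If the early scan already shows the full change (E = C), the shift is zero. Free of the assumed score, and writing f for the fraction of C reached at the early scan, the shift is k(1 - f)/25 of C: 4% for k = 1 and f = 0, 10% for k = 5 and f = 0.5, and 20% for k = 5 and f = 0.

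**The case against.** The best defence is that the sentences can be read together. The opening exception is specific and can be taken to qualify the later general reference to EOT/EOS procedures, which is itself prefaced by a condition of feasibility. The exception is tied to the EOT/EOS Visit, not to Visit 7, and the follow-up sentence keeps protocol procedures running. A reader might infer that discontinuers lose their Week 24 scan altogether. The documents do not support that: on its words, the follow-up sentence appears to retain the Visit 7 CT, and SAP 5.4.5 then selects it over an early scan.

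This narrows the problem but does not remove it. Nothing in 7.1.1, 6.8.1 or the SoA says that the exception governs the later sentence. Section 7.1.1 also lists reasons for which a participant must be withdrawn from any further study procedure, so it is not clear which discontinuers remain in follow-up to Visit 7.

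It is also fair to say that LMK is summarised descriptively, that no hypothesis is tested, and that no threshold for LMK exists which a shift of this size could cross. That limits the consequence and is accepted.

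**Conclusion.** The conflict within 7.1.1 is real, and neither 6.8.1 nor the SoA settles it. It reaches the analysis through the Table 10 window, and only for the small group identified above. With 1 to 2 such participants, the mean LMK change moves by about 0.04 to 0.32 points, or 0.05 to 0.4 SE, under the assumed changes and SD.

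Two stronger readings should be resisted. A reader might apply the shift to all five planned drop-outs. That figure (0.2 to 0.8 points) is an upper case, because the 20% allowance may include rescued participants, INCS users and people who do have a Visit 7 scan. A reader might also infer from the matching wording in 6.8.1 that surgery cases distort the Week 24 LMK; they do not, since their values are imputed by the same rule whether or not a scan is taken. The primary endpoint, based on nasal polyp score, is not affected.

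This is worth correcting because it concerns how a key secondary endpoint is collected and assigned to a visit, but the expected numerical effect is small.

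**What to change.** In the protocol, reconcile the sentences of 7.1.1 with each other, with 6.8.1 and with the SoA, so that sites follow one CT rule for discontinuers. State explicitly whether the Visit 7 CT already on the schedule applies to those still in follow-up at Week 24.

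In the SAP, narrow the Week 24 CT window in Table 10 around day 169, for example to the nasal endoscopy window of days 141 to 224. State in 4.4.1.1 that a CT at an early EOT/EOS assessment outside that window is not a Week 24 LMK value and is handled by the missing-data rules. Both SAP changes are needed together: the 4.4.1.1 sentence alone would contradict Table 10 as it stands.

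The cost is wording plus one window change, with no scan beyond the existing schedule. A few more Week 24 LMK values will be imputed. With the example window, a CT on days 225 to 265 would belong to no visit unless the Week 52 window, which starts at day 266, is adjusted as well. The SAP part can be made even if collection under the protocol is already under way.
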